the Same Day as Treatment Period 2.....87

Table 9: Clinical Criteria for the Diagnosis of Anaphylaxis.....97

Table 10: Severity of Unsolicited Adverse Events98

Table 11: Intensity of Solicited Local Adverse Events.....99

List of Figures

Figure 1: Study Overview47

List of Abbreviations

Abbreviation	Definition
ACS	Abnormal, clinically significant
AE	Adverse event
AESI	Adverse event of special interest
ALT	Alanine aminotransferase
APTT	Activated partial thromboplastin time
AST	Aspartate aminotransferase
C1-INH	C1-esterase inhibitor
CSL	CSL Behring GmbH
DVT	Deep vein thrombosis
eCRF	Electronic case report form
eDiary	Electronic diary
F1 + 2	Prothrombin fragments 1 and 2
FDA	Food and Drug Administration
GCP	Good Clinical Practice
GGT	Gamma glutamyl transferase
CCI	CCI
HAE	Hereditary Angioedema
HIV	Human immunodeficiency virus
HBV	Hepatitis B virus
HCV	Hepatitis C virus
ICH	International Conference on Harmonisation
ICF	Informed consent form
IEC	Independent ethics committee
CCI	CCI
INR	International normalized ratio
IRB	Institutional review board
IRT	Interactive response technology
ITT	Intent to Treat
IU	International unit
IV	Intravenous
MedDRA	Medical Dictionary for Regulatory Activities
C	CCI
PE	Pulmonary embolism
PEF	Peak expiratory flow
C	CCI
PP	Per-protocol

Abbreviation	Definition
CCI	CCI
SAE	Serious adverse event
SAP	Statistical analysis plan
SC	Subcutaneous
CCI	CCI
SUSAR	Suspected unexpected serious adverse reaction
TEAE	Treatment-emergent adverse event
TEE	Thromboembolic event
CCI	CCI
U	Unit
VAS	Visual analog scale
CCI	CCI

1 Introduction

1.1 Background

Hereditary angioedema (HAE) is a rare genetic disorder with 3 known types (I, II, and III) [Rosen et al 1965; Bork et al 2000]. Type I and II HAE are autosomal dominant inherited disorders, which are associated with a deficiency in C1-esterase inhibitor (C1-INH) [Donaldson and Evans 1963]. In type I HAE (common form genotype), an impaired synthesis of a normal and functionally active C1-INH molecule occurs [Rosen et al 1965]. This causes a reduction in the availability of functionally active C1-INH levels to between 6% and 25% of normal [Rosen et al 1965]. In type II HAE (variant form genotype), normal levels of a functionally impaired C1-INH molecule are synthesized, but the normal form of C1-INH is considerably reduced in the circulation. Type III HAE is even less frequent and is not associated with C1-INH deficiency [Bork et al 2000]. The prevalence of type I and II HAE is estimated to be in the order of 1:50,000 [Göring et al 1998, Kunschak et al 1998], with approximately 85% of subjects having type I HAE and approximately 15% of subjects having type II HAE [Longhurst and Bork 2006].

HAE is a debilitating disease and subjects with frequent attacks are severely affected in their quality of life. Clinically, type I and II HAE are characterized by local subcutaneous (SC) / submucosal swellings of the skin (ie, edema of the extremities, facial edema, and edema of the genitals), abdominal pain attacks, and, rarely, life-threatening attacks of laryngeal edema [Bork 2008]. Attacks typically follow a course in which the edema increases for 24 to 36 hours and then slowly decreases during the following 48 to 72 hours [Zuraw 2008].

Treatment for type I and II HAE can be subdivided into the acute treatment of attacks and prophylaxis. The treatment of choice in the event of an HAE attack is the rapid replacement of the functionally missing plasma protein (ie, by intravenous [IV] administration of C1-INH concentrate or fresh frozen plasma) [Bork 2008, Gompels et al 2005, Longhurst 2005]. Recently, compounds including a kallikrein inhibitor and a bradykinin receptor antagonist have been added to the spectrum of anti-HAE medications [Cicardi et al 2010a, Cicardi et al 2010b]. Attenuated androgens or antifibrinolytics are effective in some subjects as prophylactic therapy, but may have significant side effects [Banerji et al 2008, Göring et al 1998]. Regular IV infusions of C1-INH can also be used for HAE prophylaxis [Zuraw et al 2010]. However, repeated IV administration may not be practical for all patients, and IV access can become progressively more difficult with time.

A more convenient route of administration (eg, SC) may facilitate the use of C1-INH in HAE prophylaxis. The pharmacokinetics (PK) of subcutaneously administered C1-INH in patients with HAE have been investigated using a currently available formulation [[Martinez-Saguer et al 2013](#)]. The study examined 1000 units (U) of C1-INH, in a volume of 20 mL, administered intravenously or subcutaneously; subcutaneously administered C1-INH had a bioavailability of approximately 40%, and was generally well tolerated [[Martinez-Saguer et al 2013](#)].

To further enhance the feasibility of SC administration of C1-INH, CSL830 has been developed as a human plasma-derived C1-INH concentrate that can be reconstituted in a low volume. CSL830 is being investigated for the prevention of HAE attacks.

1.2 Background Information on CSL830

1.2.1 Overview

CSL830, which is a C1-INH concentrate, is a volume-reduced formulation of the marketed product, Berinert. Berinert is currently licensed for the acute treatment of HAE attacks in more than 30 countries. The manufacturing process of CSL830 is almost identical to that of Berinert. The major difference between these 2 products is the concentration of C1-INH after reconstitution; CSL830 contains 1500 IU of C1-INH to be reconstituted in 3 mL whereas Berinert contains 500 IU of C1-INH to be reconstituted in 10 mL.

1.2.2 Nonclinical Evaluation

Berinert has been assessed in nonclinical evaluations. Berinert was well tolerated and no toxicity was observed in single-dose toxicity studies in rats and mice and a repeat dose toxicity study in rats. Information on nonclinical safety studies conducted with Berinert is available in the European Summary of Product Characteristics for Berinert and in the US Prescribing Information.

Because CSL830 has a higher local protein concentration compared with Berinert, 2 nonclinical local tolerance studies with CSL830 have been conducted in rabbits. In these 2 nonclinical studies, administration of a single injection of CSL830 (3 mL; IV, SC, intra-arterial, and intramuscular injection) revealed no findings of clinical significance and was locally well tolerated.

1.2.3 Previous Clinical Experience

Currently, clinical data are available from two studies that were conducted with CSL830: study CSL830_1001 and study CSL830_2001.

Study CSL830_1001 was conducted in healthy subjects in order to compare the safety and PK of intravenously administered CSL830 and Berinert (the currently marketed C1-INH concentrate). CSL830 had acceptable safety and local tolerability profiles. There were no adverse events (AEs) causally related to CSL830 or Berinert, and there were no clinically significant abnormalities in laboratory parameters, viral safety assessments, vital signs, physical examinations, or electrocardiogram results. No anti-C1-INH antibodies were detected in any subject. There were no thromboembolic events (TEEs), and no surrogate markers suggestive of pulmonary embolism (PE) or deep vein thrombosis (DVT) were identified. CSL830 and Berinert also had comparable PK profiles following single-dose, IV administration.

Study CSL830_2001 was conducted in subjects with HAE (type I or II) in order to characterize the PK, pharmacodynamics (PD), and safety of SC administration. Functional levels of C1-INH activity and levels of C1-INH antigen and C4 antigen were achieved with each CSL830 dosing regimen that was tested. Subcutaneous administration of CSL830 of up to 6,000 IU was tolerated with local site events. Safety events were not related to either absolute CSL830 dose or dose per body weight. There was no evidence of a dose-response relationship between the administered dose of CSL830 and the intensity of treatment-emergent adverse events (TEAEs). Inhibitory auto- antibodies to C1-INH did not develop in any of the subjects in the study. Further, there were no TEEs.

The efficacy and safety of SC CSL830 are currently being assessed in a double-blind, randomized, placebo-controlled, crossover phase 3 study (study identifier CSL830_3001) that is enrolling at least 80 subjects with HAE. During participation in CSL830_3001 subjects are randomly assigned to either a 40 IU/kg CSL830 or 60 IU/kg CSL830 treatment sequence. Each sequence consists of 2 consecutive treatment periods. Each subject receives the assigned dose of CSL830 in 1 treatment period and placebo in the other treatment period. Subjects who participate in study CSL830_3001 will be eligible to participate in this long-term safety study if they meet all eligibility criteria (see [Section 4.1](#)).

1.3 Study Overview

This is a multicenter, randomized, open-label, parallel-arm, phase 3b study to investigate the clinical safety and efficacy of subcutaneously administered CSL830 in the prophylactic treatment of HAE. [Section 3](#) presents a detailed overview of the study design and other supporting information.

1.4 Potential Risks and Benefits

Potential for Virus Transmission

CSL830 contains human plasma-derived C1-INH and, therefore, has the potential for virus transmission to recipients. However, CSL830 has a high margin of virus safety. The risk of virus transmission is minimized by stringent donor selection and screening criteria, and by reducing enveloped and non-enveloped viruses using pasteurization, nanofiltration methods, and chromatography [De Serres et al 2003].

During study CSL830_2001 (see [Section 1.2.3](#)), no new viral infections were detected in subjects who received CSL830. No changes in serology results for HIV (human immunodeficiency virus), hepatitis A virus, HBV (hepatitis B virus), HCV (hepatitis C virus) were observed from baseline to study exit.

During this 12-month safety study, evidence of potential viral transmission will be collected as part of the safety evaluations.

Immunogenicity or Anaphylactic-type Reactions

Immunologic or anaphylactic-type reactions have been rarely reported with the use of C1-INH. Antibodies against C1-INH have been identified in patients with HAE, irrespective of whether they have received C1-INH. However, the presence of antibodies against C1-INH does not appear to inhibit the activity of C1-INH [data on file at CSL; [Farkas et al 2007](#)].

The immunogenicity of CSL830 was examined as a part of study CSL830_2001 (see [Section 1.2.3](#)). C1-INH antibodies were detected for 7/18 subjects during that study; however, the presence of C1-INH antibodies was not associated with inhibition of C1-INH activity. There was no apparent relationship between the dose of CSL830 administered and the presence of C1-INH antibodies.

The development of immune reactions to CSL830 will be monitored in this study, and will include testing for and characterization of (eg, idiotyping) anti-C1-INH antibodies.

Thromboembolic Events

Thromboembolic events have been occasionally reported following the use of C1-INH, especially in patients receiving off-label high doses of up to 500 U/kg IV in the setting of cardiac surgery and extracorporeal circulation. At the recommended IV doses, a causal relationship between TEEs and the use of C1-INH has not been established.

During study CSL830_2001 (see [Section 1.2.3](#)) no TEEs were reported. Further, no subject treated with CSL830 was considered to be at risk for DVT, when assessed using a clinical model scoring system.

TEEs including DVT and PE will be monitored during this study (see [Section 8.1.2](#)).

Local Tolerance

Because of the SC route of administration and the high protein concentration of CSL830, transient local reactions may occur at CSL830 injection sites.

During study CSL830_2001, a small proportion of subjects administered CSL830 experienced local administration site reactions. The reactions were mostly mild to moderate in intensity, most resolved within 3 days.

Local reactions will be documented as part of the safety evaluation during this study.

Efficacy

Intravenous C1-INH has been demonstrated to be effective in the prevention of HAE attacks [[Zuraw et al 2010](#)]. However, the efficacy of SC C1-INH for prophylaxis of HAE attacks has not been established, but is under evaluation as a part of the pivotal study CSL830_3001 (see [Section 1.2.3](#)). As such, throughout the current study, eligible subjects will be permitted to use medication for the treatment of breakthrough HAE attacks.

Overview

This clinical study may contribute to the development of a new therapy to effectively manage HAE. Given the low probability of potential risks and the study procedures that will closely monitor the safety of study subjects, the associated risk-benefit assessment of the study is acceptable for subjects enrolled in the study.

2 Study Objectives and Endpoints

2.1 Primary Objective and Endpoints

2.1.1 Primary Objective

The primary objective is to assess the clinical safety of subcutaneously administered CSL830 in the long-term prophylactic treatment of HAE.

2.1.2 Primary Endpoints

The primary endpoints are the person-time incidence rates of each of the following:

- Adverse events leading to premature study discontinuation.
- Thromboembolic events.
- Anaphylaxis.
- HAE attacks resulting in in-patient hospitalization (where hospitalization is the consequence of the need for emergent medical care).
- Solicited AEs (injection site reactions at the CSL830 injection site) graded as severe by the investigator.
- Related serious adverse events (SAEs), other than events specified above.
- Anti-C1-INH antibodies (inhibitory or non-inhibitory).

The person-time incidence rates are the number of subjects experiencing each primary endpoint safety event during treatment with CSL830, divided by the sum of each subject's time at risk.

The primary endpoints will be assessed for Treatment Period 1, Treatment Period 2 and Treatment Periods 1 and 2 (together). The primary endpoints will also be assessed for the Extension Period (only) and for the treatment periods overall for subjects who are included in the Extension Period.

2.2 Secondary Objectives and Endpoints

2.2.1 Secondary Objectives

The secondary objectives are the following:

1. To further characterize the clinical safety of subcutaneously administered CSL830 in the long-term prophylactic treatment of HAE.
2. To characterize the clinical efficacy of subcutaneously administered CSL830 in the long-term prophylactic treatment of HAE.

2.2.2 Secondary Endpoints

1. The secondary safety endpoints are the following:
 - a. The percentage of subjects experiencing the following events: SAEs, temporally-related AEs, increased risk scores for DVT or PE, TEEs, inhibitory anti-C1-INH antibodies, or clinically significant abnormalities in laboratory assessments (ie, lab abnormalities reported as AEs).
 - b. The percentage of administrations of CSL830 resulting in solicited local AEs (discomfort [eg, pain, burning], swelling, bruising, or itching at the CSL830 injection site).
 - c. The percentage of subjects who have at least 1 solicited local AE (discomfort [eg, pain, burning], swelling, bruising, or itching at the CSL830 injection site).
 - d. The percentage of subjects who become seropositive for HIV-1/-2, HBV, or HCV.

The secondary safety endpoints will be assessed for Treatment Period 1, Treatment Period 2 and Treatment Periods 1 and 2 (together). The secondary safety endpoints will also be assessed for the Extension Period (only) and for the treatment periods overall for subjects who are included in the Extension Period.

2. Efficacy endpoints considered as secondary include the following:
 - a. The percentage of subjects who experience a time-normalized HAE attack frequency of < 1 HAE attack per 4-week period.
 - b. The percentage of subjects who are responders. “Response” is defined as a $\geq 50\%$ relative reduction in the time-normalized number of HAE attacks during treatment with CSL830, compared with the time-normalized number of attacks that is used to qualify the subject for participation in this study (see [Section 4.1.2](#) [inclusion criterion 5]).

The secondary efficacy endpoints will be assessed for Treatment Period 1, and Treatment Periods 1 and 2 (together). The secondary efficacy endpoints will also be assessed for the Extension Period (only) and for the treatment periods overall for subjects who are included in the Extension Period.

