3.3 Planned Study Duration

Treatment Period 1 and Treatment Period 2

The duration of the study for an individual subject is expected to be up to 58 weeks. This estimation is based on:

- A Screening Period lasting up to 4 weeks (≤ 28 days), as needed.
- Two treatment periods totaling 52 weeks (367 days \pm 2 days).
- A Follow-up Period lasting 2 weeks (14 days \pm 3 days).

The overall study duration (ie, from the first subject’s first Screening Visit to the last subject’s Follow-up Visit) is planned to be 26 months, but will depend on recruitment.

Extension Period (Optional)

The Extension Period (88 weeks) followed by the Extension Period follow-up (2 weeks) will begin at first subject first visit in the Extension Period and result in an anticipated total study duration of up to approximately 146 weeks for participating subjects. Subjects who have any Extension Period visits that occur within 6 weeks before the study end date will be handled as completers. These subjects will attend the final study visit (Extension Period Week 88) in place of their next study visit or telephone contact and will receive follow-up telephone contact (Extension Period Week 90 ± 3 days). Subjects who roll-over into the Extension Period prior to the Treatment Period 2 Follow-up Visit will be regarded as completers. All subjects who are not withdrawn from the study will be considered completers of the study.

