3.5 Planned Number of Subjects

The study plans to enroll subjects who complete participation in CSL830_3001. Additional subjects who have not participated in study CSL830_3001 will be enrolled so that the total number of subjects randomized is approximately 110.

Assuming that up to 10% of subjects withdraw before the completion of the study, 100 subjects are planned to complete the study.

Subjects from the United States who have completed Treatment Period 1 and Treatment Period 2 according to the study protocol are eligible to enroll in the Extension Period. Approximately 50 of these subjects are anticipated to enroll in the Extension Period.

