4.1 Planned Analyses

The data from Treatment Period 1, Treatment Period 2, and Extension Period will be analyzed and presented jointly, unless specified otherwise.

For subjects who are not participating in the Extension Period, the End of Study Visit will be at Week 53. For subjects who are participating in the Extension Period, the End of Study Visit will be at Week 88.

All summary tables will be presented by treatment groups 40 IU/kg CSL830, 60 IU/kg CSL830, and ≥ 40 IU/kg CSL830 unless specified differently. Events occurring under 80 IU/kg will be summarized in the ≥ 40 IU/kg CSL830 treatment group and otherwise listed only.

Subject disposition will be summarized for all subjects who provide informed consent/assent (as appropriate). Demographic and subject characteristics will be summarized using the ITT and Safety Populations.

All safety data will be summarized using the Safety Population. The analysis of the safety endpoints will be by actual CSL830 treatment (40 IU/kg CSL830, 60 IU/kg CSL830, or ≥ 40 IU/kg CSL830) the subject was taking when the event occurred, unless specified otherwise. In the analysis as treated, a subject contributes events or assessments to each treatment received, e.g. a subject randomized and treated with 40 IU/kg and up-titrated and treated with 60 IU/kg will be displayed in both treatments as well as displayed once in the ≥ 40 IU/kg treatment.

The efficacy endpoints considered as secondary will be summarized using the ITT and PP Populations. CCI

CCI

CCI

Continuous variables will be described by using the mean value with the respective 95% confidence intervals (CI) [only for efficacy variables]; standard deviation; range; 25th, 50th (median), and 75th percentiles; and counts of missing and non-missing values. The geometric coefficient of variation will be expressed as a percentage and the geometric mean and respective 90% CI will be calculated for CCI. The 90% CI for the geometric mean will be calculated by log transforming the data, calculating the lower and upper limits of the 90% CI of the mean of the log-transformed data and, subsequent back transforming the lower and upper limits. Categorical values will be described using counts and percentages. Time variables will be described by median, minimum and maximum and if applicable in addition by mean, standard deviation, 25th and 75th percentiles and graphically represented by Kaplan-Meier curves with the respective 95% CI.

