4.7.2.1 Method of analysis for secondary safety endpoints

The AE tables will comprise two type of tables, one for number of subjects experiencing a particular AE, percentage of subjects based on the Safety Population, and number of events and the other type of tables for number of events per subject-injections and number of events per subject-years, the latter giving exposure-adjusted rates (per injection and per year).

All AEs

A summary of all AEs will be given presenting: number and percentage of subjects with AEs, with temporally-related AEs, with suspected ADRs, with SAEs, with related AEs, AE leading to discontinuation based on AE start date with subcategories for “related” and “not related”, with each severity and with each outcome of AEs. Analogue summaries will be provided for only SAEs and for only non-serious AEs.

The following tables will be generated for all AEs (including unsolicited AEs and solicited AEs):

- Incidence of subjects with AEs by SOC and PT.
- Incidence of subjects with SAEs by SOC and PT.
- Incidence of subjects with AEs by severity, SOC, and PT.
- Incidence of subjects with AEs by relationship to investigational product, SOC, and PT.
- Incidence of subjects with AE leading to discontinuation based on adverse event start date by SOC and PT.
- Incidence of subjects temporally-related AEs by SOC and PT.
- Incidence of subjects with suspected ADRs by SOC and PT

- Incidence of subjects with AE matching the PT ‘Embolic and Thrombotic Events’ (SMQ) by SOC and PT overall and split by subjects with versus without indwelling venous catheter. Events identified by this SMQ PT are reviewed by CSL Behring to assist in identification of cases of TEEs.

- Incidence of subjects with AE High Level Term ‘Sepsis, Bacteraemia, Viraemia and Fungaemia NEC’ (by SOC and PT, overall and split by subjects with vs. without venous catheter). Events identified by this High Level Term are reviewed by CSL Behring to assist in identification of cases of sepsis and/or bacteremia events.

- Incidence of subjects with SMQs to identify anaphylaxis defined as severe and clinically relevant systemic allergic reaction with sudden onset and rapid progression by SOC and PT. AE terms screened to assist in identification of cases of anaphylaxis were selected for review using the following SMQs:
 - SMQ = ‘Anaphylactic reaction (SMQ)’ and selection = ‘Broad’.
 - SMQ = ‘Anaphylactic/anaphylactoid shock conditions (SMQ)’ and selected = ‘Broad’.

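### The SAP replaces the protocol's by-period percentages of subjects with safety events by one figure pooled over about 54 weeks for some subjects and up to about 142 weeks for Extension subjects

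*Protocol*

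**What the plan says.** Protocol 2.2.2 sets the reporting windows for the secondary safety endpoints: "The secondary safety endpoints will be assessed for Treatment Period 1, Treatment Period 2 and Treatment Periods 1 and 2 (together". It adds the Extension alone, and all treatment periods overall for subjects in the Extension. Protocol 11.3.3.2 repeats the three windows. Protocol 11.3.3 limits both Extension summaries to subjects enrolled in the Extension.

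SAP 4.1 sets a different default: "The data from Treatment Period 1, Treatment Period 2, and Extension Period will be analyzed and presented jointly, unless specified otherwise". For secondary safety, SAP 4.7.2.1 describes two types of AE table. The first is "one for number of subjects experiencing a particular AE, percentage of subjects based on the Safety Population", together with the number of events. The second gives events per injection and per subject-year. No table for Treatment Period 1 (TP1), Treatment Period 2 (TP2) or the two together (TP1+2) is specified for any secondary safety endpoint.

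SAP 4.14 lists two changes from the protocol: the joint presentation, and the analysis of Extension and non-Extension subjects together. It gives no reason for either. The one rationale nearby, that few subjects are expected to have a dose increase, supports analysis by actual dose and not the merging of periods.

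On the size of the Extension, Protocol 3.5 says: "Approximately 50 of these subjects are anticipated to enroll in the Extension Period".

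**The concern.** A percentage of subjects with at least one event has no time unit, so it means something only if the observation window is known and common. Here the windows differ by a factor of about 2.6. Who gets the long window is not random either: only US subjects who completed TP2 may enter the Extension. The pooled percentage therefore depends on how many US subjects roll over and how long the Extension runs, as well as on the product. It is neither a one-year risk nor the risk over the whole Extension, and it cannot be set directly beside a percentage from a one-year study.

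The SAP recognises unequal follow-up elsewhere. SAP 4.12 points out that the primary person-time rates allow for differing observation times. SAP 4.6.3.1 gives the responder analysis cumulative 6- and 12-month windows, separately for Extension and non-Extension subjects. The secondary percentages of subjects with an event have neither protection.

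The endpoints exposed to this are those counted cumulatively per subject: SAEs, temporally-related AEs, TEEs, laboratory abnormalities reported as AEs, at least one solicited local AE, and the overall (any-time) antibody percentage.

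**Working it through.** **Follow-up lengths.** The inputs are in Protocol 3.3: screening of up to 4 weeks; 52 weeks for TP1+2; "A Follow-up Period lasting 2 weeks"; and an Extension of 88 weeks with 2 weeks of follow-up.

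- The plan's own totals reproduce: 4 + 52 + 2 = 58 weeks without the Extension, and 4 + 52 + 88 + 2 = 146 weeks with it. The protocol states 58 weeks and an "anticipated total study duration of up to approximately 146 weeks for participating subjects".
- From Day 1, leaving out screening: 52 + 2 = **54 weeks** without the Extension and 52 + 88 + 2 = **142 weeks** with it. The ratio is 142/54 = 2.63. A rest period of up to 30 days before the Extension is not counted.
- SAP 4.7 assigns AEs arising in each follow-up period to the preceding treatment period, so these windows are the ones in which AEs are counted.

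**Direction.** Take a fixed set of subjects, such as the SAP's ≥ 40 IU/kg column. Any subject with an event in TP1+2 also has one in the all-period count, and some subjects may have their first event in the Extension. The pooled percentage is therefore at least as large as the TP1+2 percentage. This needs no model.

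**Size.** The documents give no event rates, so the size is illustrative. Assumptions: constant hazard; no dropout; 50 of about 110 randomized subjects in the Extension; the other 60 followed for 54 weeks. For a 54-week risk p and Extension subjects followed for T weeks:

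- risk in Extension subjects: q = 1 − (1 − p)^(T/54)
- pooled percentage: (60p + 50q)/110

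Example with p = 5% and T = 142: q = 1 − 0.95^(142/54) = 12.6%, and the pooled figure is (60 × 5.0 + 50 × 12.62)/110 = 8.5%, which is 1.69 times p.

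| 54-week risk p | q at 142 weeks | Pooled | Ratio to p | Ratio if the Extension averages 44 weeks (T = 52 + 44 + 2 = 98) |
|---|---|---|---|---|
| 1% | 2.6% | 1.7% | 1.73 | 1.37 |
| 5% | 12.6% | 8.5% | 1.69 | 1.35 |
| 10% | 24.2% | 16.5% | 1.65 | 1.34 |
| 20% | 44.4% | 31.1% | 1.55 | 1.30 |
| 40% | 73.9% | 55.4% | 1.39 | 1.23 |
| 70% | 95.8% | 81.7% | 1.17 | 1.12 |

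If the base is the 100 planned completers instead of 110, the full-length ratios run from 1.80 (p = 1%) down to 1.18 (p = 70%).

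The comparator gives every subject the 2-week TP2 follow-up. Subjects who roll straight into the Extension have none. Using 52 weeks for all 50 entrants moves the ratio at p = 5% from 1.69 to 1.72, which is immaterial.

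**Onset pattern.** If every first event fell within the first 54 weeks, the ratio would be 1.0. Injection-site reactions that begin early in treatment would lie nearer to that limit than the table suggests.

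**Where the mechanism does not act.** The percentage of administrations followed by a solicited AE adds to its numerator and denominator together: 5% in both phases stays 5%. DVT/PE risk scores are summarized at each visit (SAP 4.7.5). Viral serology is listed only (SAP 4.7.2.3). Events per injection and per subject-year already carry exposure in the denominator.

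**The case against.** The strongest reply has four parts.

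First, the change is open: SAP 4.14 declares both the joint presentation and the mixing of populations. That is right. A reader might infer that the SAP departs from the protocol unnoticed, and the documents do not support that. What stands is that no justification is given.

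Second, exposure is handled elsewhere. SAP 4.7.2.1 adds events per injection and per subject-year. SAP 4.7.1 gives subject-level person-time rates with 95% intervals for TEEs, anaphylaxis, severe solicited AEs, antibodies, and related SAEs not covered by another primary endpoint. SAP 4.4.1 summarizes exposure in three ways. So a claim that safety cannot be compared across unequal follow-up goes too far. These outputs still do not yield the protocol's by-period percentages: event rates can be driven by a few subjects with repeated events, and the primary rates do not cover all SAEs, temporally-related AEs or all solicited AEs at subject level.

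Third, not every endpoint is affected. A reader might infer that all secondary safety endpoints are crude subject percentages inflated by the Extension. The documents contradict this for the percentage of administrations, the by-visit DVT/PE scores and viral serology. Antibodies are also shown by visit, so only their overall figure is exposed.

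Fourth, Extension-length percentages are not foreign to the protocol, which asks for all-period figures in Extension subjects. That is also right. The defect is mixing them with non-Extension subjects and dropping the by-period tables.

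**Conclusion.** The concern holds for the cumulative percentages of subjects only. Followed as written, the SAP would not produce the protocol's TP1, TP2 and TP1+2 percentages for these endpoints, nor the Extension-only and all-period percentages restricted to Extension subjects. The single figure it gives mixes about 54 and up to about 142 weeks of follow-up. For the same subjects, that figure cannot be lower than the TP1+2 one.

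The size rests on assumption. With constant hazard, no dropout, a full-length Extension and 50 of 110 subjects entering it, the pooled value is about 1.7 times the TP1+2 value for rare events and about 1.2 times for common ones. Each of these conditions may fail: the protocol allows for up to 10% withdrawal, subjects close to the study end date take the final Extension visit early, and early-onset events inflate less. A reader should not take 1.7-fold as an expected result.

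**What to change.** In SAP 4.1 and 4.7.2, for the cumulative subject-level endpoints named above:

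1. Tabulate the percentages for TP1, TP2 and TP1+2, with all Safety Population subjects treated in that period as denominator. Make TP1+2 the main table, running from first injection to the Week 53 Visit plus the TP2 follow-up where it applies.
2. Tabulate Extension-only and all-period percentages with Extension entrants as denominator, as the protocol requires.
3. Use the joint pooling of Extension and non-Extension subjects only for exposure-adjusted rates.

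If the sponsor prefers to omit any of the protocol's windows, SAP 4.14 should give the reason.

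This does not equalise follow-up between the as-treated dose columns, because subjects with a dose increase still contribute part of their time to more than one column. The dose columns should therefore be read with the exposure-adjusted rates.

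Cost: SAP wording and extra runs of the existing AE table programs with date cuts. SAP 4.7 already has a rule for assigning AEs between visits to a period, so no new data are needed.
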